13.2.4. Renal Monitoring Plan

- **Serum Cystatin C:** GFR is a requisite component of renal testing to evaluate glomerular and nephron integrity. While “gold standard” methods of determining GFR (eg, infusions of inulin, iohexol, iohalamate, or technetium 99m-diethylenetriamine pentaacetic acid [^{99m}Tc-DTPA] with timed blood and urine assessments) can be employed, these methods are cumbersome and are often reserved for renal physiology laboratories at specialized centers [Guignard 2004, Stevens 2007]. In clinical practice, assessments of GFR have more typically relied upon determination of creatinine clearance during 24-hour urine collections or calculation based on nomograms using only serum creatinine. It is generally acknowledged that 24-hour urine collection in children is inaccurate and impractical due to compliance issues [Guignard 2004]. Calculation of GFR using only measurement of serum creatinine has long been standardized for children [Schwartz 1987]. However, because it is both filtered and secreted by the kidney, serum creatinine is acknowledged to be relatively imprecise and insensitive marker of renal damage [Herget-Rosenthal 2007, Schwartz 2007]. Moreover, serum creatinine is subject to variation based on endogenous and exogenous factors. This problem is particularly concerning in boys with DMD because the majority of creatinine in serum is derived from muscle [Wang 1996] and boys with DMD have decreased serum creatinine concentrations due to reduced muscle mass. A review of baseline serum creatinine values among the 38 boys with DMD participating in the ataluren Phase 2a study indicates low serum creatinine values (median 0.3, range 0.1-0.5 mg/dL). Additional sources of variability for boys with DMD may include ingestion of creatine (a substrate for creatinine production) [Escobar 2005] and treatment-mediated alterations in muscle fragility [Mendell 1989].

As an alternative to assessing GFR based on serum creatinine, serum cystatin C offers substantial advantages in the context of this protocol. Cystatin C is a low-molecular-weight [~13 kDa] proteinase inhibitor derived from all cells that is filtered by the glomerulus and degraded in the renal tubules [Herget-Rosenthal 2007]. The serum cystatin C concentration is almost solely dependent upon GFR and appears relatively unaffected by muscle mass or other conditions. An additional advantage is that circulating cystatin C changes more rapidly in response to multiple types of renal injury than creatinine [Herget-Rosenthal 2007]. Methods for measuring cystatin C are standardized and the correlations between serum cystatin C and GFR have been derived and confirmed in large studies involving healthy children and adults and those with renal dysfunction [Dharnidharka 2002, Grubb 2005, Zappitelli 2007]. Based on these considerations, values of serum cystatin above 1.33 mg/L should prompt diagnostic evaluation and interruption/modification of study drug if required per protocol.

- **Serum Creatinine:** Given the widespread clinical familiarity with serum creatinine as a marker of renal dysfunction and as a monitoring tool for nephrotoxins in clinical practice [Gilead 2002, Gilead 2006, Novartis 2005], characterization of serum creatinine provides an appropriate frame of reference relative to other experiences. Because most participating boys with DMD are expected to have low normal values of serum creatinine due to reduced muscle mass, any values higher than the normal range may be cause for concern. Caveats regarding interpretation of serum creatinine in boys with DMD (particularly if there are

food- or treatment-induced changes in serum creatinine values) dictate that an increase in serum creatinine above the age-specific normal range should prompt reevaluation of other safety parameters and potential interruption/modification of study drug dosing.

- **Serum Blood Urea Nitrogen:** Considering its role in maintaining urine-concentrating ability, urea has major importance in renal physiology and its clinical measurement as a marker of renal dysfunction is long established. In the context of nephrotoxicity, elevations in BUN suggest disruption of tubular integrity [Vonderscher 2007]. In the nonclinical mouse studies of ataluren in which nephrosis was observed, BUN was elevated in some of the affected animals, confirming that this marker should also be measured in clinical studies of ataluren. Monitoring serum BUN, like monitoring creatinine, provides an additional frame of reference relative to other markers assessed within this study and in other studies of known nephrotoxicants. However, an elevation in BUN is not a specific signal of renal tubular injury, but also may reflect compromised renal tubular blood flow due to depressed cardiac output, medications, or dehydration [Guignard 2004, Stevens 2007]. For these reasons, a BUN increase ≥ 1.5 x ULN should prompt a review of potential pre-renal, renal, and post-renal causes for the abnormality as well as consideration of potential interruption/modification of study drug dosing.
- **Urine Protein:Creatinine and Urine Protein:Osmolality Ratio:** Proteinuria can be an early marker for renal injury in experimental models [Amin 2004] and is commonly observed with even modest clinical decreases in renal function [National Kidney Foundation 2002]. Glomerular disease (eg, diabetic nephropathy) is often associated with albuminuria due to defects in exclusion of plasma proteins in the glomerular filtrate. Tubular injury (eg, as observed in mice receiving ataluren) more often leads to increases in low-molecular-weight proteins (eg, beta-2 microglobulin, β 2-microglobulin, α 1-microglobulin retinol-binding protein, lysozyme) as tubular protein catabolism is compromised or proteins of injury are produced [Guignard 2004, Stevens 2007]. Because mice that developed nephrosis while receiving ataluren had proteinaceous material in the renal tubules on histological examination, monitoring of urine protein in humans receiving ataluren is additionally warranted.

Traditional methods of urine protein screening are only semiquantitative, are relatively insensitive, and are confounded by exogenous substances and subjective interpretation [Kim 2007]. The presence of urinary protein may be masked in dilute urine or exaggerated in concentrated urine. For these reasons, a quantitative method of accessing proteinuria is planned in this study. Two methods will be assessed: urinary protein concentration relative to urinary creatinine concentration [Ginsberg 1983, Schwab 1987] and urinary protein concentration relative to urine osmolality [Wilson 1993, Morgenstern 2003]. These methods of screening, using spot urine samples, have been found to be as accurate as and more practical than quantification of urine protein during a 24-hour collection. Values for protein:creatinine of ≥ 0.2 mg/dL:mg/dL and of protein:osmolality of ≥ 0.15 mg/L:mOsm/kg have been established as abnormal [Morgenstern 2003]. While measurement of protein:creatinine is generally the preferred method in children [Morgenstern 2003], it is possible that low urinary creatinine excretion in boys with DMD may falsely elevate protein:creatinine ratios. For this reason, confirmed evidence that both measures are

abnormal should stimulate further evaluation and intervention. Follow-up methods such as urine electrophoresis may be useful in discriminating among the types of proteins present and may suggest a site of injury (eg, an albumin-specific pattern with glomerular damage versus a diffuse multiple low-molecular-weight protein pattern with tubular damage) [Stevens 2007]. Confirmed proteinuria should prompt consideration of interruption/modification of study drug dosing.

- **Urine Blood:** Blood in the urine may indicate pathology of the renal parenchyma or of the urinary collecting system (eg, ureters, bladder, and urethra). Like proteinuria, hematuria is commonly found in patients with minimal changes in GFR due to renal (particularly glomerular) dysfunction [National Kidney Foundation 2002]. Confirmed, persistent evidence of urinary blood by dipstick and/or microscopic examination will prompt further evaluation. Ultrasound or other imaging can evaluate for a potential renal cause for bleeding. Urology consultation can be obtained to assess for post-renal sources of hematuria. Clotting function and use of drugs that may impair platelet function will be reviewed. Confirmed, persistent hematuria in the absence of a post-renal source of bleeding or a bleeding diathesis will prompt potential interruption/modification of study drug dosing.
- **Serum Electrolytes:** Assessments of serum electrolytes (sodium, chloride, potassium, bicarbonate, magnesium, calcium, and phosphorus) provide information regarding renal function that may supplement more primary assessments. Derangements in serum concentrations may reflect altered tubular handling of these ions. With worsening renal function, hyperphosphatemia and hypocalcemia may develop and reductions in serum bicarbonate or elevations in potassium may suggest an impaired ability of proximal tubules or collecting ducts to maintain acid-base balance [National Kidney Foundation 2002]. Given the cardiovascular and neurological consequences of severe derangements of serum potassium, calcium, or magnesium, evaluation of these ions is important to avoid potential secondary complications. Because transient Grade 1 alterations in the concentrations of electrolytes are very unlikely to be associated with significant secondary side effects, alterations to \geq Grade 2 are considered appropriate to prompt potential interruption/modification of study drug dosing.
- **Renal Ultrasound:** In considering the markers to be used for decision-making within the study, renal ultrasound is proposed because it is the central imaging modality for assessing the anatomy of the kidneys and urinary tract in children. The test can detect changes in kidney size, assess parenchymal cystic or mass lesions, evaluate the renal vasculature, and assess the collecting system [Avni 2004]. Renal ultrasound is a routine component of diagnostic algorithms for follow-up of serum or urinary abnormalities suggesting renal dysfunction [Barratt 2004] and will be among the diagnostic testing performed for this protocol as part of the assessment for such findings. It is safe, painless and convenient, providing advantages over contrast-enhanced computed tomography (CT) scanning (which has contrast-mediated nephrotoxicity and radiation risks) and magnetic resonance imaging (MRI) (which requires contrast administration and potential sedation in young children). Obtaining a baseline ultrasound enhances the sensitivity of subsequent ultrasonography, offering context for any potential abnormalities emerging during study drug treatment. An

end-of-study ultrasound offers further reassurance that the kidneys remain anatomically normal at the completion of this protocol.

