6.3. Safety Monitoring and Study Drug Dose Interruption/Modification

6.3.1. Laboratory Abnormalities and Adverse Events Requiring Evaluation and Potential Drug Interruption/Modification

Patients must be monitored closely for adverse events or laboratory abnormalities during the course of the study.

For adverse events or laboratory abnormalities, the investigator will use judgment in determining whether the event or abnormality is clinically significant, whether diagnostic evaluation is warranted, and whether potential interruption of study drug treatment is appropriate. In general, life-threatening (Grade 4) or severe (Grade 3) adverse events or laboratory abnormalities should be considered clinically significant, although recurrent or persistent moderate events (Grade 2) may also be considered clinically significant in certain circumstances. Reference should be made to the Common Terminology Criteria for Adverse Events (CTCAE), Version 3.0 (see http://ctep.cancer.gov/protocolDevelopment/electronic_applications/docs/ctcae3.pdf) for grading the severity of adverse events and laboratory abnormalities.

Table 2 provides information on actions to be taken in the event that abnormalities are noted in specified laboratory parameters. Thresholds are provided for interrupting study drug immediately, for interrupting study drug after confirmation of a value beyond the threshold, or for continuing study drug while evaluating for potential drug-related toxicity. For adverse events or laboratory abnormalities not listed in **Table 2**, the investigator should use his/her judgment in determining whether the event or abnormality is clinically significant, whether diagnostic evaluation is warranted, and whether potential interruption of study drug is appropriate.

Table 2. Safety Monitoring Parameters and Actions To Be Taken

Organ System and Laboratory Parameter	Stop Study Drug Immediately, Confirm Abnormal Value, and Then Start Work-Up	Stop Study Drug After Confirming ^a Abnormal Value, and Then Start Work-Up	Continue Study Drug, Confirm Abnormal Value, and then Start Work-Up ^a
Hepatic			
Serum total bilirubin	≥Grade 3 (≥3.0 x ULN)	Grade 2 (1.5 – 3.0 x ULN)	---
Serum GGT	≥Grade 3 (≥5.0 x ULN)	Grade 2 (>2.5 – 5.0 x ULN)	---
Serum ALT			↑ of > 150 U/L with stable or ↓ CK
Renal			
Serum cystatin C	>2.00 mg/L	>1.33 – 2.00 mg/L	---
Serum creatinine	≥ Grade 2 (≥1.5 x ULN for age)	Grade 1 (>ULN – 1.5 x ULN for age)	---
Serum BUN	≥3.0 x ULN	≥1.5 – 3.0 x ULN	---

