Urine protein: urine creatinine (spot)	---	>0.40 mg:mg	---
Urine protein: urine osmolality (spot)	---	>0.30 mg/L:mOsm/kg	---
Urine blood (by dipstick)	4+ (Large)	3+ (Moderate)	2+ (Small)
Serum electrolytes	Grade 3-4	Grade 2	Grade 1
Serum Na ⁺ , high	>155 mmol/L	>150 – 155 mmol/L	---
Serum Na ⁺ , low	<130 mmol/L	---	---
Serum K ⁺ , high	>6.0 mmol/L	>5.5 – 6.0 mmol/L	---
Serum K ⁺ , low	<3.0 mmol/L	---	---
Serum Mg ²⁺ , high	>1.23 mmol/L	---	---
Serum Mg ²⁺ , low	<0.4 mmol/L	<0.5 – 0.4 mmol/L	---
Total serum Ca ²⁺ , high	>3.1 mmol/L	>2.9 – 3.1 mmol/L	---
Total serum Ca ²⁺ , low	<1.75 mmol/L	<2.0 – 1.75 mmol/L	---
Serum phosphorous	<0.6 mmol/L	<0.8 – 0.6 mmol/L	---
Serum HCO ₃ ⁻	<11 mmol/L	<16 – 11 mmol/L	---

^a Laboratory abnormalities may be confirmed immediately or at the next scheduled clinic visit based on investigator judgment. Abbreviations: ACTH = adrenocorticotropic hormone, ALT = alanine aminotransferase, BUN = blood urea nitrogen, Ca²⁺ = calcium, CK = creatine kinase, GGT = gamma glutamyl transferase, HCO₃⁻ = bicarbonate, K⁺ = potassium, Mg²⁺ = magnesium, Na⁺ = sodium, ULN = upper limit of normal

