**Table 2: Safety Monitoring Parameters and Actions to be Taken**

Organ System and Laboratory Parameter	Stop Study Drug Immediately, Confirm Abnormal Value, and Then Start Work-Up	Stop Study Drug After Confirming a Abnormal Value, and Then Start Work-Up	Continue Study Drug, Confirm Abnormal Value, and then Start Work-Up a
Hepatic			
Serum total bilirubin	≥Grade 3 (≥3.0 x ULN)	Grade 2 (1.5 – 3.0 x ULN)	---
Serum GGT	≥Grade 3 (≥5.0 x ULN)	Grade 2 (>2.5 – 5.0 x ULN)	---
Serum ALT			↑ of >150 U/L with stable or ↓ CK
Renal			
Serum cystatin C	>2.00 mg/L	>1.33 – 2.00 mg/L	---
Serum creatinine	≥Grade 2 (≥1.5 x ULN for age)	Grade 1 (>ULN – 1.5 x ULN for age)	---
Serum BUN	≥3.0 x ULN	≥1.5 – 3.0 x ULN	---
Urine protein: urine creatinine (spot)	---	>0.40 mg:mg	---
Urine protein: urine osmolality (spot)	---	>0.30 mg/L:mOsm/kg	---
Urine blood (by dipstick)	4+ (Large)	3+ (Moderate)	2+ (Small)
Serum electrolytes	Grade 3-4	Grade 2	Grade 1
Serum Na + , high	>155 mmol/L	>150 – 155 mmol/L	---
Serum Na + , low	<130 mmol/L	---	---
Serum K + , high	>6.0 mmol/L	>5.5 – 6.0 mmol/L	---
Serum K + , low	<3.0 mmol/L	---	---
Serum Mg 2+ , high	>1.23 mmol/L	---	---
Serum Mg 2+ , low	<0.4 mmol/L	<0.5 – 0.4 mmol/L	---
Total serum Ca 2+ , high	>3.1 mmol/L	>2.9 – 3.1 mmol/L	---
Total serum Ca 2+ , low	<1.75 mmol/L	<2.0 – 1.75 mmol/L	---
Serum phosphorous	<0.6 mmol/L	<0.8 – 0.6 mmol/L	---
Serum HCO 3 	<11 mmol/L	<16 – 11 mmol/L	---

a Laboratory abnormalities may be confirmed immediately or at the next scheduled clinic visit based on investigator judgment.

**Abbreviations:** ALT = alanine aminotransferase, BUN = blood urea nitrogen, Ca2+ = calcium, CK = creatine kinase, GGT = gamma glutamyl transferase, HCO3 = bicarbonate, K+ = potassium, Mg2+ = magnesium, Na+ = sodium, ULN = upper limit of normal

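### Protocol Table 2 and Section 13.2.4 give different proteinuria triggers, so sites may act differently on the same confirmed values

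*Protocol*

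**What the plan says.** **Protocol Section 6.3.1 and Table 2.** The text says that thresholds are provided, among other purposes, "for interrupting study drug after confirmation of a value beyond the threshold". Proteinuria has two rows. The row "Urine protein: urine creatinine (spot" sample) carries a cut-off of more than 0.40 mg:mg. The osmolality row carries ">0.30 mg/L:mOsm/kg". Both sit in the column for stopping drug after confirmation and then starting a work-up. No wording links the two rows.

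**Protocol Section 13.2.4.** On definitions: "Values for protein:creatinine of ≥ 0.2 mg/dL:mg/dL and of protein:osmolality of ≥ 0.15 mg/L:mOsm/kg have been established as abnormal". It then notes that low urinary creatinine in boys with DMD may falsely raise the creatinine-based ratio, and goes on: "For this reason, confirmed evidence that both measures are" "abnormal should stimulate further evaluation and intervention". On drug action: "Confirmed proteinuria should prompt consideration of interruption/modification of study drug dosing".

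**SAP Section 5.7.2 and SAP Table 2.** The SAP reprints the protocol table, including the row "Urine protein: urine osmolality (spot" sample), with the same 0.40 and 0.30. It says the summary of pre-defined monitoring abnormalities follows that table. SAP Section 1 gives the SAP precedence over the protocol where they conflict.

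**The concern.** Renal safety has its own monitoring plan in this study, prompted by mouse findings and earlier renal laboratory abnormalities. Section 13.2.4 is introduced as the rationale for the decision parameters. For proteinuria, though, the reason it gives is a reason to require both ratios, and the table does not require both.

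An investigator with a confirmed, isolated rise in protein:creatinine finds a stop instruction in one place. In the other, the investigator finds a warning that this ratio alone may mislead. Two sites could handle the same values differently, each with protocol text in support.

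The choice can reach the primary safety data. Under Protocol Section 8.1.1 a laboratory finding becomes an adverse event when it needs intervention, or investigation beyond a repeat test. SAP Section 5.7.1 tabulates renal events that led to special diagnostic work-up. If the trigger for work-up varies by site, so may that table and the number of interruptions.

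**Working it through.** The documents give no rate, count or distribution for proteinuria, so there is no planned figure to reproduce. The check compares the passages and then tests the logic.

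**1. Side by side** (PC = protein:creatinine, PO = protein:osmolality)

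| | Table 2, protocol and SAP | Protocol 13.2.4 |
|---|---|---|
| PC | > 0.40 | ≥ 0.2, described as abnormal |
| PO | > 0.30 | ≥ 0.15, described as abnormal |
| Combination | separate rows, no joint condition | both |
| Action | stop after confirmation, then work-up | evaluate and intervene; consider interruption or modification |

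Cut-off ratios: 0.40/0.2 = 2.0 and 0.30/0.15 = 2.0.

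**2. Does one rule contain the other?** Write Rule A (Table 2) as PC > 0.40 or PO > 0.30. Write Rule B (13.2.4) as PC ≥ 0.2 and PO ≥ 0.15.

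| PC | PO | A | B |
|---|---|---|---|
| 0.50 | 0.10 | yes | no |
| 0.10 | 0.35 | yes | no |
| 0.30 | 0.20 | no | yes |
| 0.50 | 0.35 | yes | yes |
| 0.30 | 0.10 | no | no |

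Each rule flags cases that the other misses, so neither is simply a stricter form of the other.

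**3. Does the conflict survive if 0.2 and 0.15 are only background?** Apply the both-measures condition at the Table 2 cut-offs (Rule C: PC > 0.40 and PO > 0.30). The pair 0.50 and 0.10 still meets A and fails C. The and/or conflict therefore does not depend on how the lower values are read. Under this reading C lies wholly inside A.

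**4. Can the size be derived?** No. As an illustration only, assume log-normal ratios with log-SD 0.6, median PC 0.10 or 0.15, and median PO 0.75 times median PC. Assume a correlation of 0.5 to 0.95, PC then inflated 1- to 2-fold for low creatinine, and one sample from each of 220 boys. The 220 is the approximate upper bound in Protocol Section 10.1; all the other inputs are assumed.

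| Patients flagged, of 220 | Range over the assumptions |
|---|---|
| Rule A | about 3 to 72 |
| Rule B | about 10 to 69 |
| A only | about 0 to 33 |
| B only | about 6 to 45 |

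The direction also changes. With median PC 0.10, correlation 0.95 and no inflation, A flags about 3 and B about 22. With median PC 0.15, correlation 0.5 and 2-fold inflation, A flags about 72 and B about 64.

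**5. Which outputs can move?** The SAP laboratory summary counts against 0.40 and 0.30 row by row, so Section 13.2.4 does not enter it. Interruptions, and adverse events created by a work-up, follow what the site did and can move.

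**The case against.** The strongest reply is that the operative text can be identified. Section 13 is rationale, Section 13.2.3 sends readers to Section 6.3.1 for actions, and the SAP adopts Table 2. That lowers the risk of divergent conduct but does not remove it. Section 13.2.9 asks for the recommendations to be viewed flexibly, and a stated reason for requiring both ratios cannot serve as the rationale for separate rows.

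Several narrower replies stand in whole or in part:

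- **Cut-offs.** The 0.2 and 0.15 values come from a cited publication as a definition of abnormal and are not labelled stopping thresholds. An action level above the limit of normal is no contradiction in itself; Table 2 acts on BUN only from 1.5 times ULN. The cut-off conflict is therefore arguable. Even so, no other definition of abnormal appears beside the both-measures condition. For cystatin C, creatinine and BUN, the level in 13.2.4 matches the lower Table 2 action level.
- **Either.** Table 2 does not use that word; it is inferred from separate rows with no linking condition.
- **Action.** Section 13.2.4 also speaks of potential interruption for creatinine and BUN, so the softer wording is not peculiar to proteinuria. The and/or logic is the firmest part of the conflict.
- **Timing.** SAP Section 5.2 records the sponsor's decision to discontinue the study, so a protocol clarification can change little in conduct.

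A reader might infer that the SAP's renal laboratory count depends on which passage is used. It does not, because SAP Section 5.7.2 ties it to Table 2. A reader might also take the protocol to say that protein:creatinine is falsely high in this disease. It says only that this may happen.

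**Conclusion.** The protocol is wrong as written: it contradicts itself on when proteinuria triggers action. The passages differ on and/or logic and strength of action, and arguably on cut-off by a factor of two for each ratio. With 0.2 and 0.15 taken as the meaning of abnormal, neither rule contains the other. With those values set aside, the and/or conflict remains.

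The consequence is limited to site behaviour and what follows from it: interruptions, and renal adverse events entered because a work-up was started. It is tempting to conclude that requiring both ratios must flag fewer patients. That follows only if the cut-offs are the same. With the lower values the effect can go either way, and the documents supply nothing from which to estimate it. The simulated ranges rest wholly on assumed distributions and show only that the direction is open.

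**What to change.** **Protocol.** Reconcile Section 13.2.4 with Table 2 on three items: whether one ratio or both are needed, at what cut-off, and what action follows. Which rule is right is a clinical decision and is not proposed here. If conduct is already closed, the study report should state the discrepancy and, where site records show it, which rule was applied.

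**SAP.** Keep the two separate ratio counts in the Table 2 summary and add one row for patients exceeding both. State whether both must be exceeded on the same urine sample and whether confirmation is required. Patients flagged on protein:creatinine without the other ratio are then the protein:creatinine count minus the joint count. This shows how many flags rest only on the ratio that the protocol calls potentially unreliable.

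**Cost.** A short clarification and one table row. Urine protein, creatinine and osmolality are already collected under Protocol Section 7.8, so no new data are needed.
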